## 9.2. Setting and subjects

### 9.2.1. Duration of study

Planned duration of enrollment/data collection: Patients will be enrolled for 6 years after approval of Repatha Inj., and data will be collected until 12 weeks of last subject's enrollment.

## 9.2.2. Selection and number of study institutions

Amgen will prepare a list of potential institutions/investigators who can prescribe Repatha Inj. in post-marketing settings. Based on this data, Amgen will visit each of the potential institutions prior to study initiation to evaluate feasibility of the institutions and to confirm the potential investigators' interest in and willingness for study participation. Study institutions will be selected based on the results of these pre-study site visits. Before the study begins, initiation visits will be carried out to

complete site trainings for the protocol and other study specific procedures. At the initiation visits, it will be emphasized that all eligible patients should be enrolled according to the protocol.

### 9.2.3. Subject eligibility

### 9.2.3.1. Inclusion criteria

- HoFH patient treated with Repatha Inj. according to the approved therapeutic indications, dosage, and administration in post-marketing settings
- Patient who voluntarily provided written informed consent

### 9.2.3.2. Exclusion criteria

- Patient who did not provide written informed consent
- There are no other exclusion criteria.

### 9.2.4. Matching

Not applicable

### 9.2.5. Baseline period

Before the first dose of Repatha Inj. is administered, baseline data (e.g., clinical laboratory tests, concomitant medication) will be collected (the latest time point prior to the first Repatha Inj. dose).

### 9.2.6. Follow-up

Each patient will be followed up from the first Repatha Inj. dose to Week 12 of treatment (window period for data collection: 10-14 weeks), death, or lost to follow-up (e.g., patient transfer to another hospital), whichever is earlier.

### 9.3. Endpoints

### 1) Primary endpoint

The primary endpoint is the incidence rate of AEs(including device related AEs)/ADRs observed or reported to the investigator during the follow-up period. All AEs will be classified using MedDRA. If sufficient data is collected, seriousness and causal relationship to drug or device can be also analyzed.

- 2) Secondary endpoints
- Efficacy measurement; change in LDL-C measured as part of routine clinical practice from baseline to the end of follow-up
- Patient characteristics (for details, see Section Error! Reference source not found..)
  - o Demographic information and medical history
  - Diagnosis of hypercholesterolemia
  - Concomitant medication prior to study participation
  - o Other concomitant medication

## 9.3.1. Observation and data collection

See Figure 1 below for study diagram.

Figure 1 Overview of variables to be collected during the study

Procedure	Week 1	Weeks 2-11	Week 12±2 weeks
Patient enrollment for evolocumab treatment	Administe X	er Repatha Inj. according to pre	escription
CRF (bseline)	Х		
CRF (Repatha Inj. dose and number of doses administered) a - Cumulative data through follow-up	<		$\longrightarrow$
CRF (LDL-C) b - Cumulative data through follow-up	←		$\longrightarrow$
CRF (safety)			

a. All information verifiable through follow-up will be collected.

b. There is no established procedure to collect LDL-C data in this study. Only the information verifiable through follow-up will be collected.

A patient who provides written informed consent and meets the inclusion/exclusion criteria will be considered eligible for enrollment in this study. Once the patient is enrolled, baseline data including demographic information should be collected in the CRF. Repatha Inj. treatment and LDL-C measurement information will continue to be collected during the follow-up period. AEs and other safety information will be also collected during the follow-up period.

At baseline, the following patient characteristics and variables will be collected in the CRF.

- Diagnosis of HoFH: duration of disease, family history, physical examination findings (tendinous xanthoma, cutaneous tuberous xanthoma), genetic test
- Demographic information: gender, date of birth, height, body weight, waist line, inpatient/outpatient
- Medical history: coronary artery disease (surgery; coronary artery bypass graft [CABG], percutaneous coronary intervention [PCI]), allergy, concomitant underlying disease (myocardial infarction, angina pectoris, heart failure, cerebral infarction [including psychogenic embolism], cerebral hemorrhage, peripheral arterial disease [PAD], hypertension [systolic and diastolic blood pressure measurements], diabetes mellitus [including impaired glucose tolerance, HbA1c], cognitive deficits [cerebrovascular/Alzheimer's disease type]), liver function (Child-Pugh class; A, B, or C), kidney function (chronic kidney disease [CKD], eGFR), and other medical conditions that may affect the safety and efficacy of evolocumab treatment.
- Concomitant medication:
  - ✓ Prior (8 weeks before baseline) and concomitant medication: statins (drug name, dose, duration of treatment), other medications for hypercholesterolemia
  - ✓ Concomitant treatment for hypercholesterolemia: medical diet, medical exercise, LDLapheresis (8 weeks before baseline, date), apheresis, and other treatment
  - ✓ Other therapeutic drugs for concomitant disease: low-dose aspirin, warfarin, non-Vitamin K antagonists, oral anticoagulants, estrogen, steroids, or non-steroidal anti-inflammatory drugs for hypertension, diabetes mellitus, heart attack, angina pectoris, and arrhythmic disorder
- Lifestyle: smoking (past, current), alcohol consumption, exercise.

For safety assessment, all AEs and other safety information (e.g., pregnancy and lactation), if possible, will be collected through follow-up.

For efficacy assessment, LDL-C levels measured as routine clinical practice will be collected from baseline (the latest time point prior to the first Repatha Inj. dose) to the end of follow-up. Although LDL-C measurement cannot be required as part of the study procedures, LDL-C level monitoring is recommended as standard of care. Drugs administered over the period of 8 weeks prior to baseline will be collected as concomitant medication.

## 9.3.2. Assessment of exposure

Not applicable

### 9.3.3. Assessment of results

AEs (including SAEs and ADRs) and other safety information will be collected throughout the followup period, if possible, in the CRF and applicable safety reporting forms. Clinical laboratory test values and LDL-C levels measured during visits will be collected in the CRF at baseline (Week 0), at Week 12 (range: 10-14 weeks), or at the end of follow-up if the subject did not complete the 12 week treatment.

### 9.3.4. Assessment of covariates

Not applicable

### 9.3.5. Validity and reliability

Not applicable

### 9.4. Data source

The source of data to be used in this study is the patient's medical records. In addition, data will be also collected through the CRFs completed by the investigator. Laboratory test values will be measured at each institution according to the institutional standard practice.

### 9.5. Number of subjects

Amgen plans to recruit in a consecutive manner 10 patients who meet the inclusion/exclusion criteria for this study for 6 years after approval of Repatha Inj. in Korea.

Based on the low diagnosis rate and prevalence of HeFH ( $1/160,000 \sim 1,000,000$  individuals), number of subjects estimated is approximately 10 subjects.

### 9.6. Data management

Data will be managed according to applicable criteria and data cleaning procedures. Once the procedure for data quality management is completed, database will be locked. The original CRFs will be retained by Amgen Korea.

## 9.6.1. Obtaining data files

Not applicable

## 9.6.2. Linking data files

Not applicable

## 9.6.3. Data quality checking and confirmation

A validated data system will be used for data collection. Data will be managed according to applicable standard operating procedure (SOP) under the supervision of Amgen Korea. Once retrieved, the CRF will be checked for data integrity. Any missing data should be completed or accounted for by the investigator. The data obtained from the CRF will be transferred to the study database and verified. Exposure, results, and all other variables observed and measured at the institution will be collected through the data system. Data validation program will be used for standardized error checking. For logical discrepancies or obvious errors identified, a query will be sent to the investigator for confirmation and correction.

The investigator and study staff should verify the data against medical records, and the investigator will confirm and guarantee, by signing, the accuracy and integrity of the data corresponding to the information contained in the medical records. In addition, overlapping patients will be checked. Details of quality assurance will be described in the data management plan.

## 9.7. Data analysis

## 9.7.1. Planned analysis

## 9.7.1.1. Interim analysis

According to local regulations, interim analyses will be performed for periodic reporting. Periodic reports should be submitted to the MFDS every 6 months for the first 2 years and every year thereafter until the end of re-examination period.

## 9.7.1.2. Primary analysis

Not applicable

## 9.7.1.3. Final analysis

Final analysis is planned to be performed once all study data are collected and cleaned (after database locking).

## 9.7.2. Planned analysis methods

## 9.7.2.1. Analysis sets

Data collected will be analyzed in the following analysis sets. For those subjects who are prematurely withdrawn, reasons for withdrawal will be described.

-Safety set: subjects who had at least one dose of the study drug and were followed up for safety at least once.

-Efficacy set: subjects in the safety set who were assessed for efficacy at least once.

## 9.7.2.2. General considerations

All analyses will be performed with SAS 9.4 or higher version. In principle, two-sided statistical tests will be performed at a significance level of 5%, and up to two digits after the decimal point will be presented in summary statistics.

## 9.7.2.3. Missing or incomplete data and lost to follow-up

In the event of missing data, observations will be used as they are for analysis, without corrections.

## 9.7.2.4. Analysis of primary, secondary, and exploratory endpoints

## 9.7.2.4.1. Disposition of subjects

All subjects collected will be summarized as below:

CRF retrieved	Number of subjects: XXX (100%)	
	Number of subjects excluded from the safety set:	XX
	Reason) XXXXXX	XX
Safety set	XXX (a %)	
	Number of subjects excluded from the efficacy set:	′ xx
	Reason) XXXXXX	XX
Efficacy set	XXX (b %)	

Percentage will be calculated for a and b (relative to the number of subjects collected).

#### 9.7.2.4.2. Subject characteristics

For demographic information of study subjects, categorical variables will be summarized with frequency and percentage, and continuous variables will be summarized with mean, SD, SE, median, Q1, Q3, minimum, and maximum. Subject information will be collected to identify patterns of drug use and will not be used as covariates for statistical analysis.

- Demographic information: gender (male, female), age (year), adult (≤65 years old, >65 years old), children (≤18 years old), pregnancy and lactation (yes, no), concomitant disease (yes, no), past medical history (yes, no), height, body weight, prior medication (yes, no)
- Lifestyle: status of smoking (ex-smoker, current smoker, non-smoker), alcohol consumption (current drinker, non-drinker), status of exercise
- All medical history collected will be standardized according to system organ class (SOC) and preferred term (PT). Based on the standardized SOC and PT, number of subjects (%) and number of events will be presented for past medical history.
- Past medical history: coronary artery disease (surgery; CABG, PCI), allergy, concomitant disease (myocardial infarction, angina pectoris, heart failure, cerebral infarction [including psychogenic embolism], cerebral hemorrhage, PAD, hypertension [systolic and diastolic blood pressure measurements], diabetes mellitus [including impaired glucose tolerance, HbA1c], cognitive deficits [cerebrovascular/Alzheimer's disease type]), liver function (Child-Pugh class; A, B, or C), kidney function (CKD, eGFR), and other medical conditions that may affect the safety and efficacy of evolocumab treatment.
- Other concomitant medication: all drugs, other than evolocumab, administered during the study period including enrolment visit; brand name, start date, end date, dose per administration, frequency of administration, route of administration, purpose of administration (indication), etc.
- Diagnosis of hypercholesterolemia: duration of disease (date of diagnosis), family history, physical examination findings (tendinous xanthoma, cutaneous tuberous xanthoma), genetic test (HeFH or HoFH)
- All drugs collected will be classified into prior or concomitant medication and will be standardized according to anatomical main group (Level 1) and therapeutic subgroup (Level 2) using World Health Organization Anatomical Therapeutic Chemical Code (WHO ATC code).

Based on the standardized Level 1 and Level 2, number of subjects (%) and number of events will be presented for prior and concomitant medication.

### 9.7.2.4.3. Analysis of primary endpoint (safety)

AEs occurring during the study (including drug/device AEs and SAEs) will be summarized with number of subjects, number of events, and incidence rate.

### 9.7.2.4.4. Analysis of secondary endpoints (efficacy)

- Percent (%) change in LDL-C at Week 12 from baseline
- Absolute change in LDL-C at Week 12 from baseline

#### 9.7.2.5. Sensitivity analysis

Sensitivity analysis is not planned for this study.

#### 9.7.2.5.1. Subgroup analysis

Not applicable

### 9.7.2.5.2. Stratified analysis

Not applicable

### 9.7.2.5.3. Sensitivity analysis for residual confounding factors and bias

Not applicable

### 9.7.2.5.4. Other sensitivity analysis

Other sensitivity analysis is not planned for this study.

### 9.7.3. Analysis of safety endpoints

See Section Error! Reference source not found..

### 9.8. Quality control

Quality control will be performed by confirming that data management is operated according to data management SOP, all quality control results, including violations and measurements, are documented/reported, and violations, if applicable, are corrected as appropriate.

### 9.9. Limitation in study methodology

Because of its prospective, observational nature, this study is more greatly affected by bias than interventional clinical trials are. Below is the summary of methods to reduce common limitations and errors identified in this type of study.

· Missing and incomplete data including lost to follow-up

The investigator should be given clear guidelines for CRF completion for this study to ensure that he/she makes every effort to collect complete data.

- Selection bias, information bias, and confounding factors
  - Most patients treated with Repatha Inj. in post-marketing settings in Korea are expected to enroll in this study. This will be helpful in restricting selection bias.

- Amgen will prepare a list of potential institutions/investigators who can prescribe Repatha Inj. to HoFH patients in post-marketing settings. Based on this data, Amgen will visit each of the potential institutions prior to study initiation to evaluate feasibility of the institutions and to confirm the potential investigators' interest in and willingness for study participation. Study institutions will be selected based on the results of these pre-study site visits.
- Amgen will ask all known physicians who prescribe Repatha Inj. If a physician who was asked to conduct the study for Repatha Inj does not want to participate in the study, Amgen will record the reason in writing.
- Before the study begins, initiation visits will be carried out to complete site trainings for the protocol and other study specific procedures. At the initiation visits, the rareness of the disease will be explained, and the investigators will be asked to make every effort to enroll all eligible HoFH patients in a consecutive manner.
- There is a possibility that patients enrolled in this study (e.g., patients who will be treated with Repatha Inj.) are likely to have a severer form of the disease than those HoFH patients who are not prescribed Repatha Inj. (patients not included in the study). This confounding by indication bias would limit the generalization of safety and efficacy results.
- Analysis results should be interpreted with sufficient understanding of these study limitations. Of those, the most significant limitation is due to the very small number of patients to be enrolled. The very limited number of patients would limit the power of inference of this study because of lack of accuracy in estimation.

### 10. Patient protection

### 10.1. Informed consent

This study requires informed consent in order to collect medical information from patients treated with Repatha Inj. under conditions of routine clinical practice. The investigator cannot have a patient participate in the study without obtaining informed consent from that patient. Prior to study participation, the patient's written informed consent should be obtained and documented. At the time of informed consent, the patient will sign and date the written informed consent form (ICF). The original signed ICF should be retained by the investigator, and a copy of the signed ICF will be provided for the subject.

### 10.2. Institutional Review Board

This study will be conducted in compliance with applicable local regulations as well as Institutional Review Board (IRB) regulations. If necessary by regulation, an approval will be obtained prior to study initiation from an adequately established IRB. In addition, if necessary by regulation, the investigator is responsible for notifying the IRB of the safety information/cases subject to expedited reporting.

### 10.3. Confidentiality

The investigator should ensure that the patient confidentiality is maintained in the documents submitted to Amgen Korea.

The patient's medical information obtained as part of this study is confidential and should not be disclosed to a third party except for cases described below. The investigator/institution will allow Amgen and its representative, MFDS, and other regulatory authorities to have direct access to source document/data. This access can be provided during study related monitoring, audit/inspection, and IRB/MFDS review. Presentation of study results should be conducted

according to applicable local regulations, and personal information contained in the medical information should be kept confidential in these presentations.

### 11. Collection of safety information and product complaints

### 11.1. Definitions of safety events

### 11.1.1. Adverse event

An AE is any unintended medical event occurring to a patient treated with a drug, regardless of causal relationship to the relevant treatment. Therefore, an AE can be any undesirable and unintended sign (e.g., laboratory test abnormalities), symptom, or disease occurring during treatment with the drug, and does not necessarily have to have a causal relationship to the relevant drug.

AEs are defined as:

- Exacerbation of a pre-existent condition or underlying disease, or
- An event related to drug withdrawal (e.g., development of a new symptom)

The investigator is responsible for assessing the causal relationship of an AE to Amgen Korea products before reporting the event to Amgen Korea.

Device (e.g., injection) related AEs are associated with device application and include insufficient or inappropriate instructions for application, malfunction, intentional misuse/overuse of device, or application error.

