## 8. Study questions and objectives

## 8.1. Primary objective

The primary objective of this study is to assess the incidence rate of AEs (including device related AEs) and ADRs for up to 12 weeks in patients who are prescribed Repatha Inj. in post-marketing settings (see Section 11 for definitions of terms). In addition, profiles of AEs and ADRs will be analysed.

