## 11.1.3. Other safety findings

Other safety information (irrespective of AE relationship) is as follows:

- Amgen drug product related medication error, accidental or intentional overdose, misuse, or overuse
- Exposure during pregnancy and lactation
- Transmission of infectious agents
- Reported use of the drug for purposes other than the approved indications, including off-label use
- Occupational exposure
- Lack or loss of the intended efficacy of the drug

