## 11.1.4. Product complaints

A product complaint is any written, electronic, or oral notification claiming defects of a product or device associated with its identity, quality, durability, reliability, safety, efficacy, or function after it is released by Amgen or its distributor or partner to be distributed to market or hospitals. These include drugs or devices provided and/or repackaged/modified by Amgen; drugs or devices include investigational products.

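### Section 11.1.1 describes device-related AEs by listing device faults and use errors, so a fault that harms nobody can be read as an AE in the primary endpoint

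*Protocol*

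**What the plan says.** Section 9.3 of the protocol sets the primary endpoint: "The primary endpoint is the incidence rate of AEs(including device related AEs)/ADRs observed or reported to the investigator during the follow-up period". Section 9.7.2.4.3 carries this into the analysis: "AEs occurring during the study (including drug/device AEs and SAEs) will be summarized with number of subjects, number of events, and incidence rate". The primary objective, in the synopsis and in section 8.1, also includes device-related AEs and points the reader elsewhere for the terms: "see Section 11 for definitions of terms". What counts is therefore decided in section 11.

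Section 11.1.1 opens with the general definition: "An AE is any unintended medical event occurring to a patient treated with a drug, regardless of causal relationship to the relevant treatment". It goes on to speak of signs, symptoms and diseases. Its last sentence turns to device-related AEs, ties them to application of the device, and says that they "include insufficient or inappropriate instructions for application, malfunction, intentional misuse/overuse of device, or application error".

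Two neighbouring sections cover similar ground:

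- Section 11.1.3 lists other safety information, which applies whether or not an AE is involved. One item is "Amgen drug product related medication error, accidental or intentional overdose, misuse, or overuse".
- Section 11.1.4 defines a product complaint as a notification "claiming defects of a product or device associated with its identity, quality, durability, reliability, safety, efficacy, or function".

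Section 11.2 names AEs, product complaints and other safety information as three kinds of safety event, all to be recorded. The sample form in Appendix C has options for an AE, for another safety finding, for either of these accompanied by a product complaint, and for a product complaint alone.

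**The concern.** The items in the last sentence of 11.1.1 are not signs, symptoms or diseases. Poor instructions, a malfunction, a misuse or an application error may lead to a medical event or to nothing at all. The sentence says that device-related AEs include these items. It does not say that device-related AEs are medical events caused by them. It therefore conflicts with the general definition in the same section.

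The conflict reaches the primary endpoint, because device-related AEs are named in the objective, the endpoint and the analysis. Suppose an injector jams, the dose is wasted and the patient has no symptom. An investigator who follows the last sentence of 11.1.1 records an AE. One who follows 11.1.4 records a product complaint alone. The first enters the AE incidence and the second does not, although the same thing happened to both patients.

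The wording governs what is entered on the CRF at the site, so the protocol is the place to settle it. An analysis plan written later can only work with what sites chose to record as AEs.

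**Working it through.** The protocol states no figure on this point, so there is nothing to reproduce. The check is a comparison of definitions, followed by simple arithmetic on the planned sample.

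**Definitions side by side, for an occurrence with no medical consequence**

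| Occurrence | General AE definition, 11.1.1 | Last sentence of 11.1.1, read literally | Other section that fits |
|---|---|---|---|
| Device malfunction | Not an AE | Device-related AE | 11.1.4 (defect of function or reliability) |
| Misuse or overuse of the device | Not an AE | Device-related AE | 11.1.3, if device misuse is taken as drug-product misuse |
| Application error | Not an AE | Device-related AE | 11.1.3, if taken as a medication error |
| Inadequate instructions | Not an AE | Device-related AE | No clear match |

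The second and third columns disagree in every row, and no passage settles which one prevails. The overlap in the last column is partial. Malfunction fits 11.1.4 and is not listed in 11.1.3. Misuse and error fit 11.1.3, although its wording concerns the drug product.

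**Effect on the primary count**

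Inputs:
- Planned number of patients, n = 10 (section 9.5).
- No hypothesis is tested (section 7.3) and no confidence interval will be given (synopsis, Data analysis), so the observed figures are the result.
- Assumptions: all 10 patients enter the safety set, and incidence is read as the proportion of patients with at least one AE.

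Shift per patient whose only recorded event is a harmless fault: 1/n = 1/10 = 10 percentage points.

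Illustration: if 2 patients have a medical AE, the incidence is 2/10 = 20%. With one further patient who has only a harmless fault, it becomes 3/10 = 30%. The starting value of 2 is chosen for illustration and is not taken from the protocol.

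A harmless fault in a patient who also has a medical AE leaves the subject-level incidence unchanged but adds to the number of events.

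**How often this might arise**

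The protocol gives no fault rate. Let q be the assumed probability that a patient has such a fault, independently across patients. The chance of at least one such patient among 10 is 1 − (1 − q)^10:

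| Assumed q | Expected patients (10q) | Chance of at least one |
|---|---|---|
| 1% | 0.1 | 9.6% |
| 2% | 0.2 | 18.3% |
| 5% | 0.5 | 40.1% |
| 10% | 1.0 | 65.1% |

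These are upper figures for a change in the incidence, since the incidence moves only if the affected patient has no medical AE and the site records the fault as an AE.

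**The case against.** The best defence is that device-related AEs are a subset of AEs. The sentence stands under a definition that requires a medical event, so that condition carries over and the list merely names causes. Other parts of the protocol support this reading: section 9.3 speaks of causal relationship to drug or device, and the Appendix C form asks about relationship to the product or device. Both treat the device as a possible cause of an event. This is plausible and probably what was meant. It does not dispose of the point, because the sentence does not say it and a site following the words as written would count the fault.

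A second defence is practical. The form can record an AE together with a product complaint, AE terms are coded in MedDRA, and with about 10 patients a malfunction reported as an AE should be visible by its term. Section 9.9 promises clear CRF guidelines, and section 9.6.3 provides for queries. All of this helps, but none of it says whether a fault without harm is an AE.

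Third, one patient in 10 is worth 10 percentage points for any kind of event, and the fault rate is unknown. That is correct. The arithmetic shows what a single misclassification does, not that one is likely.

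A reader might also draw three stronger conclusions, which the documents do not support:

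- That real injuries would be lost from the count. An injury is an AE on any reading of 11.1.1, and section 11.2 requires AEs, complaints and other safety information all to be recorded.
- That 11.1.3 and 11.1.4 both claim the malfunction. Section 11.1.3 does not list it. Since 11.1.3 applies regardless of AE status, overlap with it is not in itself a contradiction.
- That the form forces a choice between AE and complaint. It has a combined option.

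**Conclusion.** The point holds as a wording defect with a direct route into the primary endpoint. The last sentence of 11.1.1 conflicts with the general definition above it and can be read as counting device faults and use errors that harmed nobody. The same occurrence also fits 11.1.4 or, for misuse and error, 11.1.3, so sites may classify it differently.

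Its size is 10 percentage points of subject-level AE incidence for each patient whose only recorded event is such a fault. This assumes that all 10 planned patients are analysed; with fewer, the step is larger. Whether it occurs at all depends on a fault rate that the documents do not give and on how sites read the sentence. The error runs towards a higher incidence. No test result is at risk, because none is planned. What is affected is the meaning and consistency of the descriptive figure that the study exists to report.

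**What to change.** Reword the last sentence of section 11.1.1 along these lines:

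> *A device-related AE is an AE (an unintended medical event) associated with use of the device, including one caused by inadequate instructions, malfunction, misuse or overuse, or application error.*

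Add two rules there and in the CRF completion guidelines:

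1. A device fault or use error without a medical event is recorded only under 11.1.3 or 11.1.4, whichever applies, and is tabulated on its own line outside the AE incidence.
2. A device fault or use error with a medical event is counted once as an AE. Where a complaint also applies, it is recorded through the combined option already on the Appendix C form.

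The cost is a few sentences in the protocol, a note for sites and one extra table line. The form needs no change and no safety information is lost. The reported AE incidence may be slightly lower than under the literal reading.
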